### 3.7 Allocation

CMHCs and patients are randomized through a computerized randomization sequence. We do not stratify during randomization at the CMHC level. When randomizing patients, we stratify for presence of psychosis or not (current), presence of substance use or not (current) and age ( $\geq 50$  or not), as there is evidence these variables can impact sleep or treatment outcome (47,75,76). Only the facilitators, assessors, and research team (i.e., not CMHCs, local trainers, providers, or patients) are privy to which CMHCs and patients are allocated to which TranS-C treatment condition (Adapted versus Standard TranS-C). CMHC providers, local trainers, and patients know whether their patients have been randomized to receive the immediate or delayed treatment. The facilitator informs the local trainer once a patient can start having sessions, who then informs the provider. In the immediate condition, the provider is asked to begin sessions as soon as possible. In the delayed condition, the provider is asked to wait until after the patient has completed the post-delay assessment (i.e., approximately four weeks in the Adapted condition or eight weeks in the Standard condition).

### 3.8 Sample Size

In the conceptualization of this study, the sample size goals for the Implementation Phase and the TTT phase combined were 96 providers and 576 patients (including 20% for attrition). During the conduct of the Implementation Phase of the study, we realized the immense value to knowledge of both the Implementation Phase and the TTT phase separately. Thus, we re-conceptualized the two phases as separate contributions. The Implementation Phase sample size remained as originally derived to power the analyses (42). The sample size of the TTT was guided by real-world factors, particularly the timeframe and budget for the study as well as the number of Generation 1 providers who are interested in recruiting, training, and supervising other providers. Additionally, in some CMHCs, many providers participated in Generation 1, leaving fewer providers to participate in Generation 2.

By the end of the TTT Phase, we project based on current recruitment numbers that we will recruit 130 patients and 60 providers. Using these sample sizes in a cluster randomized trial design, minimum detectable effect sizes were calculated for Aims 1 and 2 using Stata (77) and Aim 3 using Schoemann et al.'s (2017) application. For Aim 1, small to moderate correlations between TranS-C (vs. UC-DT) and sleep outcomes ( $rs = .37\text{-.39}$ ) and intraclass correlation (ICC) of 0.30 were estimated using data from a prior trial (35). The coefficient of variation of cluster size was estimated as 0.72, based on the anticipated ratio of standard deviation of cluster size to mean cluster size for CMHC patients (78). A two-sided alpha of 0.05 was used. Together, the minimum detectable effect size with a sample of 130 patients and 9 clusters was estimated at a large effect size of  $d = 0.94$ . We expect this effect size will be feasible to detect, given that a prior study with a similar aim and same primary outcome produced a similarly large effect size ( $d = 0.96$ ) (35). For Aim 2, prior studies have reported high sensitivity to change and test-retest reliability between measures of fit ( $rs = .83\text{-.85}$ ) (67). Based on the ICC estimated from similar prior provider-level studies (38,79), the ICC was assumed to be 0.20. The coefficient of variation of cluster size was estimated as 0.75, based on the anticipated ratio of standard deviation of cluster size to mean cluster size for providers (78). A two-sided alpha of 0.05 was used. Together, the minimum detectable effect size with a sample of 60 providers and 9 clusters was estimated at a medium to large effect size of  $d = 0.70$ . Although few prior studies are available, one similar trial found a medium effect size ( $d = .53$ ) (80). Because these estimates suggest we might be slightly underpowered for Aim 2, effect sizes will be considered in addition to p-values. For Aim 3, a Monte Carlo power analysis through Schoemann et al.'s

(2017) application was conducted with 1,000 replications, 20,000 Monte Carlo draws per replication, and 95% confidence intervals (81). Drawing from prior research, medium correlations ( $r = 0.30$ ) were assumed between the predictor (TranS-C condition) and mediators (acceptability, appropriateness, feasibility; (80) as well as mediators and outcomes ( $r = 0.50$ ). Small correlations ( $r = .20$ ) were assumed between the predictor and outcomes (82). The power detected for the indirect effects with a sample size of  $N = 60$  providers (i.e., for the mediators) was 0.62. As with Aim 2, because we may be underpowered to detect statistical significance at alpha = 0.05, effect sizes will be considered in addition to p-values.

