### Methods:

TTT will be implemented in nine CMHCs in California, United States (N = 60 providers; N = 130 patients) via facilitation. CMHCs are cluster-randomized by county to Adapted TranS-C or Standard TranS-C. Within each CMHC, patients are randomized to immediate TranS-C or usual care followed by delayed treatment with TranS-C (UC-DT). Aim 1 will assess the effectiveness of TranS-C (combined Adapted and Standard), compared to UC-DT, on improvements in sleep and circadian problems, functional impairment, and psychiatric symptoms for Generation 2 patients. Aim 2 will evaluate whether Adapted TranS-C is superior to Standard TranS-C with respect to Generation 2 providers' perceptions of fit. Aim 3 will evaluate whether Generation 2 providers' perceived fit mediates the relation between TranS-C treatment condition and patient outcomes. Exploratory analyses will: (1) evaluate whether the effectiveness of TranS-C for patient outcomes is moderated by generation, (2) compare Adapted and Standard TranS-C on patient perceptions of credibility/improvement and PhenX Toolkit outcomes (e.g., substance use, suicidality); and (3) evaluate other possible moderators.

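### Section 3.8: the Aim 1 detectable effect (d = 0.94) applies a cluster-trial formula to a patient-randomised contrast, and the Aim 3 power (0.62) omits county clustering although its condition is allocated by county

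*Combined protocol and SAP*

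**What the plan says.** Section 3.8 opens its calculations with: "Using these sample sizes in a cluster randomized trial design, minimum detectable effect sizes were calculated for Aims 1 and 2".

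- **Aim 1.** The inputs are an ICC of 0.30 and treatment-outcome correlations of .37-.39 (both from a prior trial), a cluster-size CV of 0.72 and a two-sided alpha of 0.05. Then: "Together, the minimum detectable effect size with a sample of 130 patients and 9 clusters was estimated at a large effect size of"; the value given is d = 0.94. Feasibility is argued from that trial: "We expect this effect size will be feasible to detect, given that a prior study with a similar aim and same primary outcome produced"; the prior value is d = 0.96.
- **Aim 2.** "Based on the ICC estimated from similar prior provider-level studies (38,79), the ICC was assumed to be 0.20", with a CV of 0.75 and correlations of .83-.85 between fit measures. The result: "the minimum detectable effect size with a sample of 60 providers and 9 clusters was estimated at a medium to large effect size of"; the value given is d = 0.70.
- **Aim 3.** A Monte Carlo mediation calculation uses correlations of .30 (condition with fit), .50 (fit with outcome) and .20 (condition with outcome). "The power detected for the indirect effects with a sample size of" 60 providers is given as 0.62. No ICC, CV or cluster count is listed. Effect sizes will be considered as well as p-values "because we may be underpowered to detect statistical significance at alpha" 0.05.

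On allocation, the Abstract says: "Within each CMHC, patients are randomized to immediate TranS-C or usual care followed by delayed treatment with TranS-C (UC-DT". Section 2 says the same of counties, and Section 3.7 lists patient-level strata. Sections 4.1 and 4.3 adjust for county as a factor. By contrast, the note to Table 2 and Section 2 place Adapted versus Standard at county level, and Section 3.3.1 names nine counties.

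**The concern.** The two contrasts have different randomisation units, and Section 3.8 treats each the wrong way round. The Aim 1 contrast is formed within counties but carries a between-county design effect. The Aim 3 predictor is constant within a county but carries none.

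N was set by practical limits, so these figures are the reader's main guide to what the sample can show. For Aim 1, 0.94 sits just under the prior effect of 0.96, which makes the trial look able to detect only an effect of that size. For Aim 3, a null mediation result reads differently at a power of 0.62 than at half that.

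**Working it through.** **Aim 1, the plan's own figure.** Section 3.8 gives N = 130, 9 clusters, ICC 0.30 and CV 0.72. The power target is not stated; 80% is assumed (1.960 + 0.842 = 2.802).

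DE = 1 + ((1 + CV²)·m − 1)·ICC. With m = 130/9 = 14.44, DE = 1 + (1.518 × 14.44 − 1) × 0.30 = 7.28. With each county split over both arms, m = 7.22 and DE = 3.99.

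| Meaning of 9 clusters | MDES, r not used | MDES, r = .37-.39, factor √(1 − r²) |
|---|---|---|
| 9 clusters and 130 patients per arm: 2.802·√(2 × 7.28/130) | 0.94 | 0.86-0.87 |
| 9 clusters, 130 patients in total: 2.802 × 2·√(7.28/130) | 1.33 | 1.22-1.23 |
| 9 counties, each in both arms: 2.802 × 2·√(3.99/130) | 0.98 | 0.90-0.91 |

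Of these layouts only the first gives 0.94, and it implies 18 clusters and 260 patients. It does not carry over to Aim 2 (m = 6.67, DE = 2.88), where 9 per arm gives 0.46-0.48 with r = .85-.83. Nine in total gives 0.65-0.69 there, nearer the stated 0.70.

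**Aim 1, for the contrast as randomised.** Assumptions: 80% power, two-sided 5%, 1:1 (the 1:1 in Section 2 concerns sites), change analysis, no provider or group clustering. MDES = 2.802 × (2/√N) × √(2(1 − ρ)), where ρ is the pre-post correlation. N = 104 is 130 less an assumed 20%; Section 3.8 gives 20% only for the original combined target.

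| ρ | MDES, N = 130 | MDES, N = 104 | Power at d = 0.48, N = 130 | Power at d = 0.48, N = 104 |
|---|---|---|---|---|
| 0.7 | 0.38 | 0.43 | 0.94 | 0.89 |
| 0.5 | 0.49 | 0.55 | 0.78 | 0.69 |
| 0.3 | 0.58 | 0.65 | 0.64 | 0.54 |

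The value 0.48 is half the prior 0.96 and is used only for illustration. A 2:1 allocation would raise each MDES by 6%.

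Provider clustering: with 130/60 = 2.17 patients per provider and CV 0.72, DE = 1 + 2.29 × ICC. At ρ = 0.5 and N = 130, an assumed provider ICC of 0.05-0.30 gives 0.491 × √1.114 = 0.52 to 0.491 × √1.687 = 0.64.

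Simulation check (3,000 replications, 130 patients in nine unequal counties, county ICC 0.30, ρ = 0.5, county as a factor): power at d = 0.49 is 0.76-0.80, and above 0.99 at d = 0.94. If county also shifts change and only a county main effect is fitted, power is 0.68-0.69 and 0.99.

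**Aim 3, the plan's own figure.** With correlations .30/.50/.20 and 60 independent providers, power is 0.64-0.67 depending on the run and on a continuous or binary predictor. The Monte Carlo error of 1,000 replications is √(0.64 × 0.36/1000) = 0.015, so 0.62 is about 1.5 standard errors from 0.643. It corresponds to a calculation without clustering.

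**Aim 3, with county clustering.** ICC 0.20 and CV 0.75 are taken from Aim 2; ICC 0.05 is an assumed lower value. Sixty providers in nine counties give m = 6.67. At ICC 0.20, DE = 1 + (1.5625 × 6.67 − 1) × 0.20 = 2.88 and effective N = 60/2.88 = 21. At ICC 0.05, DE = 1.47 and effective N = 41.

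| Method (correlations as stated, no repeated-measure gain) | ICC 0.05 | ICC 0.20 |
|---|---|---|
| Simulation, counties split 5:4 (assumed), normal reference | 0.50 | 0.31 |
| Same, 7 df | 0.38 | 0.25 |
| Design effect on the condition-to-fit path only | 0.50 | 0.28 |
| Effective N in both paths | 0.43 | 0.15 |

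Across repeat runs the ranges are about 0.36-0.52 and 0.15-0.35.

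**Aim 3, if Aim 2's correlation also applies.** With r = .83-.85, DE·(1 − r²) = 2.88 × 0.311 to 2.88 × 0.278 = 0.90 to 0.80, so the design effect is cancelled. A correlation of .30 is d = 2 × .30/√(1 − .09) = 0.63, and SE = 2·√(0.90/60) to 2·√(0.80/60) = 0.245 to 0.231. Power on the condition-to-fit path is then 0.73-0.78 (normal reference). For the indirect effect it is 0.71-0.76 if the fit-to-outcome path keeps 60 independent providers, and 0.48-0.50 if that path is deflated by 2.88 too.

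**The case against.** The strongest reply is that little turns on this. The Aim 1 error is conservative, practical factors fixed N, and Sections 3.8 and 5 already disclose low power for Aim 3 and the use of effect sizes. That limits the consequences, but what is disclosed is low power, not the missing clustering.

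On Aim 3, taking Aim 2's ICC and CV without its r = .83-.85 is one-sided. This stands: if the .30 refers to raw fit scores, the repeated-measure correlation could offset the design effect. If it already refers to change, the gain does not apply, though an ICC for ratings need not hold for change either. Section 3.8 does not say which is meant. The approximations above are also not the planned model: Section 4.1 makes county a factor rather than a level, Section 4.5 does not say how that works with a predictor constant within county, and the Aim 3 outcomes are measured on patients. They show a direction and a range, not a replacement figure.

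On Aim 1, the level to which the ICC of 0.30 refers is not stated, and clustering by provider or treatment group may remain. Both are fair, but with provider ICCs up to 0.30 the example above stays at 0.64, well below 0.94. Finally, no slip of arithmetic is shown: the fault is a formula that does not match the design, with inputs missing.

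**Conclusion.** Both figures fail to match the design, in opposite directions.

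- **Aim 1:** 0.94 should be about 0.38-0.58 with 130 patients, or 0.43-0.65 with 104, under the stated assumptions and before any provider or group clustering. A reader might infer that Aim 1 is underpowered; the error runs the other way, and the Discussion's statement that the sample may be sufficient stands. Nor does it follow that half the prior effect is comfortably detectable: power at 0.48 is 54-94%, and only 54-64% at a pre-post correlation of 0.3.
- **Aim 3:** 0.62 leaves out county clustering and is probably optimistic (0.36-0.52 at ICC 0.05 and 0.15-0.35 at ICC 0.20, with no repeated-measure gain). A reader might infer that 0.62 is an upper bound. The documents do not support that, because the correlation used for Aim 2 could cancel the design effect.

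The Aim 1 mismatch and the Aim 3 omission are clear from the text. The size of the Aim 3 loss is uncertain.

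**What to change.** - **Section 3.8, Aim 1:** restate the MDES for patients randomised within county with county adjustment. Give the power target, patient allocation ratio, attrition, pre-post correlation and any provider or group clustering. Say how .37-.39 entered the calculation, or remove it. For Aims 1 and 2, say what nine clusters means for each arm.
- **Section 3.8, Aim 3:** recalculate with condition assigned to nine counties, under the model that will be used, over a range of ICCs including 0.20, and state any repeated-measure correlation and the reference distribution. Otherwise state that 0.62 assumes independent providers and ignores county clustering, without calling it an upper bound.
- **Section 5:** keep the Aim 1 sentence and add the revised Aim 3 figure or that statement.

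The cost is one recalculation each for Aims 1 and 3 and some text. Enrolment and procedures do not change. The downside is a probably less favourable stated power for Aim 3.

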## 2 AIMS

This study aims to evaluate the implementation and effectiveness outcomes of TranS-C in the CMHCs of counties across California in the United States. As explained above, the present protocol describes Phase 2, the Train-the-Trainer Phase, of a three-part hybrid type 2 effectiveness-implementation study. The Train-the-Trainer Phase builds upon the infrastructure of the Implementation Phase (42). Specifically, during the Implementation Phase, sites are cluster-randomized by county to Adapted TranS-C or Standard TranS-C with 1:1 allocation. External expert trainers train an initial cohort of providers (i.e., Generation 1 providers) in TranS-C via facilitation. Then, within each county, patients are randomized to receive

immediate TranS-C or UC-DT from Generation 1 providers.

In the Train-the-Trainer Phase, expert trainers offer additional training for Generation 1 providers to become “local trainers” in TranS-C. Then, these local trainers train the next cohort of providers (i.e., Generation 2 providers) within their organization in TranS-C (see Figure 1). Then, within each county, patients are randomized to receive immediate TranS-C or UC-DT from Generation 2 providers. Patients treated by Generation 2 providers are referred to as “Generation 2 patients.” Sites retain their original randomization assignment to Adapted or Standard TranS-C. See below for more details on the TTT procedures.

Aims and hypotheses for the Train-the-Trainer Phase mirror the Implementation Phase (42). Parallel analyses to the Implementation Phase will allow us to test the extent to which implementation and effectiveness outcomes are maintained with TTT.

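### The Aim 2 minimum detectable effect of d = 0.70 shows no allowance for having only nine counties: on 7 degrees of freedom it is about 0.79–0.84, and power at the cited d = 0.53 is about 43–47%

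*Combined protocol and SAP*

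**What the plan says.** Section 3.8 projects the sample from recruitment to date: "we project based on current recruitment numbers that we will recruit 130 patients and 60 providers". For Aim 2, the comparison of Adapted with Standard TranS-C on provider-rated fit, it gives these inputs:

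- 60 providers in 9 clusters.
- Intraclass correlation: "the ICC was assumed to be 0.20".
- Variation in cluster size: "The coefficient of variation of cluster size was estimated as 0.75".
- Error rate: "A two-sided alpha of 0.05 was used".
- Repeated-measure correlation: "prior studies have reported high sensitivity to change and test-retest reliability between measures of fit", with r = .83–.85.

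The result is that "the minimum detectable effect size with a sample of 60 providers and 9 clusters was estimated at a medium to large effect size", given as d = 0.70. The section then cites d = .53 from one similar trial, says that "we might be slightly underpowered for Aim 2", and undertakes to weigh effect sizes along with p-values. It does not report power at 0.53.

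Two other places bear on the calculation. Section 2 says that "sites are cluster-randomized by county to Adapted TranS-C or Standard TranS-C with 1:1 allocation", and sites keep that assignment in this phase. Section 4.4 defines the Aim 2 effect of interest as a treatment-by-time interaction from post-training to post-treatment, with acceptability as the primary outcome.

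**The concern.** The arms of Aim 2 differ between counties, not within them. The calculation allows for county clustering through the intraclass correlation and the variation in cluster size, but nothing shows an allowance for estimating between-county variation from only nine units. With so few clusters, normal quantiles make the trial look more sensitive than it is.

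This is the only sensitivity figure for the primary provider outcome. A reader told that the shortfall is slight would give a null Aim 2 result more weight than it can bear. Weighing effect sizes does not remove the problem. With the standard error implied by 0.70 at 80% power (0.250, derived under working), an observed d of exactly 0.53 would have a 95% interval on 7 degrees of freedom of 0.53 ± 2.365 × 0.250, or about −0.06 to 1.12.

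**Working it through.** **Inputs from section 3.8:** N = 60, 9 clusters, ICC 0.20, CV 0.75, r = .83–.85, two-sided alpha 0.05.

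**Assumptions, because the plan is silent:**
- 80% power.
- A 4:5 county split, since nine counties cannot divide equally, with providers in proportion (26.7 and 33.3).
- Equal SDs at the two time points.
- The same design effect applied to the change score.

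**Step 1. Design effect.** The mean cluster size is 60/9 = 6.67. DE = 1 + [(1 + CV²) × 6.67 − 1] × ICC = 1 + [1.5625 × 6.67 − 1] × 0.20 = 2.88.

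**Step 2. Standard error of d.** Before any use of r, it is √[2.88 × (1/26.7 + 1/33.3)] = 0.441. It is then multiplied by one of two factors:
- √[2(1 − r)] for the change contrast, the form closest to the interaction in section 4.4: SE = 0.257 at r = .83 and 0.242 at r = .85.
- √(1 − r²) for a baseline-adjusted comparison: SE = 0.246 at r = .83 and 0.232 at r = .85.

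**Step 3. Reproduce the plan's figure.** With normal quantiles at 80% power the multiplier is 1.960 + 0.842 = 2.802. The change form gives 0.677–0.721 (0.699 at r = .84) and the adjusted form gives 0.651–0.689. With no use of r the result would be 0.441 × 2.802 = 1.24, so the correlation must have entered in some such way. The stated 0.70 fits a large-sample calculation.

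**Step 4. Seven degrees of freedom.** The two-sided 5% critical value is 2.365. A noncentral t on 7 df reaches 80% power at a noncentrality of 3.270, so the minimum detectable effect is 3.270 × SE.

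| Form | MDE, normal | MDE, 7 df | Power at 0.53, normal | Power at 0.53, 7 df |
|---|---|---|---|---|
| Change, r = .83 | 0.721 | 0.841 | 54% | 43% |
| Change, r = .85 | 0.677 | 0.790 | 59% | 47% |
| Adjusted, r = .83 | 0.689 | 0.805 | 58% | 46% |
| Adjusted, r = .85 | 0.651 | 0.760 | 63% | 50% |

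An even 30:30 split moves the change form only to 0.785–0.836.

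**Step 5. Cross-check without choosing a variance form.** If 0.70 is a normal-quantile figure at 80% power, the implied SE is 0.70/2.802 = 0.250. On 7 df the minimum detectable effect is then 3.270 × 0.250 = 0.82, and power at 0.53 is 45%.

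**Step 6. Dependence on r.** In the change form on 7 df, an assumed r of 0.70 gives 0.441 × √0.60 × 3.270 = 1.12. An assumed r of 0.50 gives 0.441 × 1 × 3.270 = 1.44. These two correlations are illustrative and do not come from the documents.

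**The case against.** *The power level is not stated, so nothing proves that normal quantiles were used.* This stands. On 7 df at 70% power the same inputs give 0.70–0.74 (change) or 0.67–0.71 (adjusted), so 0.70 could also come from a small-sample calculation at lower power. A reader might infer that 0.70 arises only from large-sample quantiles, or that it is an arithmetic error; the documents support neither. The power at d = 0.53, however, depends on the standard error and the degrees of freedom, not on the power level chosen for the detectable effect.

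*Seven degrees of freedom is not one of the plan's inputs.* Also true. It would be too strong to say that on its own inputs the trial misses d = 0.53 half the time. On the stated inputs with normal quantiles the miss rate is about 37–46%; it reaches about half or more once county-level degrees of freedom are applied.

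*Section 4.1 enters county as a fixed factor, not a level, so the model's nominal degrees of freedom are larger.* They are. But section 3.8 bases its figure on a cluster randomised design with a county design effect, and the degrees of freedom belong with that basis. A model without county-level variation in change does not justify the figure. Whether fixed county effects suit county-randomised arms is a separate question.

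*The correlation criticism is speculative.* In part. A shift in mean ratings does not by itself lower r, so one cannot infer that .83–.85 is wrong because ratings are expected to change. What stands is that a cited test-retest reliability appears to serve as the correlation across a period that includes treatment delivery, and that the result is sensitive to it.

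*The plan already discloses low power.* It does, in section 3.8 and again in the limitations (section 5), and section 3.8 says that practical constraints set the sample size. The dispute is over the size of the shortfall, not over disclosure.

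**Conclusion.** The point holds as one of statement and degree. The figure of 0.70 is consistent with a large-sample calculation at an assumed 80% power. With 7 degrees of freedom for nine county-randomised clusters and an assumed 4:5 split, the minimum detectable change is about 0.79–0.84 (0.760–0.805 if baseline-adjusted). Power at d = 0.53 is then about 43–47% (46–50% if adjusted). Normal quantiles raise it only to 54–63% across both forms, so calling the shortfall slight understates it either way.

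These figures rest on the plan's own ICC, CV and r. They also assume that all 60 providers supply both ratings: the Aim 2 calculation shows no attrition allowance, and the 20% in section 3.8 belongs to the original combined-phase target. Any loss would raise the detectable effect further.

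**What to change.** In section 3.8:

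1. State the power level, the degrees of freedom, the county split and the variance form (change or baseline-adjusted) behind the Aim 2 figure.
2. Restate the minimum detectable effect on 7 degrees of freedom for the change contrast that section 4.4 tests: about 0.79–0.84 at 80% power.
3. Report power at d = 0.53 in the same form, about 43–47%, and replace the word slightly with that figure.
4. Show the detectable effect over a range of post-training to post-treatment correlations, labelled as assumed: for example 0.79–0.84 at r = .85–.83, 1.12 at 0.70 and 1.44 at 0.50.

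The cost is a text change and a less favourable stated sensitivity. Neither the design nor the sample has to change.

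### Aim 3 power of 0.62 assumes r = 0.30 from condition to fit, but the same source is quoted for Aim 2 as d = .53 (r = .256), which gives power of about 0.51

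*Combined protocol and SAP*

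**What the plan says.** All the relevant statements are in section 3.8 (Sample Size).

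- **Aim 2.** The plan derives a minimum detectable effect of d = 0.70 from 60 providers, 9 clusters, an ICC of 0.20, a cluster-size coefficient of variation of 0.75 and two-sided alpha of 0.05. It then compares this with earlier evidence: "one similar trial found a medium effect size", given as d = .53 and attributed to reference 80.
- **Aim 3, condition to mediator.** Correlations of r = 0.30, described as medium, "were assumed between the predictor (TranS-C condition) and mediators (acceptability, appropriateness, feasibility; (80"). This is also attributed to reference 80.
- **Aim 3, other paths.** The mediator-to-outcome correlation is stated as "as well as mediators and outcomes ( $r = 0.50"). For condition to outcome: "Small correlations ( $r = .20$ ) were assumed between the predictor and outcomes (82").
- **Aim 3, method and result.** The Monte Carlo "application was conducted with 1,000 replications, 20,000 Monte Carlo draws per replication, and 95% confidence intervals (81"). "The power detected for the indirect effects with a sample size of $N = 60$ providers (i.e., for the mediators) was 0.62".

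The plan adds that Aim 3 may be underpowered at the 5% level and that effect sizes will be considered alongside p-values. The Discussion repeats this for Aims 2 and 3.

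**The concern.** The first path of the Aim 3 mediation model is the Aim 2 contrast. Sections 4.4 and 4.5 use the same comparison (Adapted versus Standard) and the same three provider ratings (acceptability, appropriateness, feasibility). A single reference is cited for the size of that effect in both places, but the size differs, and the plan gives neither a conversion from d to r nor a reason for the larger value.

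The figure of 0.62 is the only number that tells a reader how far short Aim 3 falls, and it will colour the reading of a null mediation result. Power near 0.6 and power near 0.5 are both low, but the second means that a true indirect effect of the assumed size would be missed about half the time.

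**Working it through.** **Inputs (section 3.8).** Condition to mediator r_XM = 0.30; mediator to outcome r_MY = 0.50; condition to outcome r_XY = 0.20; N = 60; 95% Monte Carlo confidence interval for the indirect effect. Comparator from reference 80: d = .53. Counties are allocated 1:1 (section 2). The split of providers between conditions is not stated, so an equal split is assumed.

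**Step 1: put both effects on one scale.** For two equal groups, r = d / √(d² + 4) and d = 2r / √(1 − r²).

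- d = .53: r = .53 / √(0.2809 + 4) = .53 / 2.069 = .256.
- r = 0.30: d = 0.60 / √0.91 = 0.63.

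An unequal split does not close the gap. With a proportion p in one group, the 4 becomes 1/[p(1 − p)], and r falls to .255 at 5:4, .251 at 60:40 and .236 at 70:30.

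**Step 2: reproduce the stated power.** A single-mediator model was simulated with the plan's inputs. Path a is the regression of mediator on condition. Path b is the regression of outcome on mediator and condition. The indirect effect counts as detected when the 95% Monte Carlo interval for a × b excludes zero (20,000 draws, 20,000 replications). With least-squares standard errors and a continuous predictor, power is 0.640. Other choices (maximum-likelihood standard errors, binary predictor) give up to 0.66. The plan's 1,000 replications carry a simulation error of √(0.62 × 0.38 / 1,000) = 0.015, so 0.62 is approximately reproduced from its stated inputs.

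**Step 3: change only r_XM.**

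| r_XM | Equivalent d | Power, N = 60 (least squares, continuous predictor) | Range over variants |
|---|---|---|---|
| 0.30 | 0.63 | 0.640 | 0.64 to 0.66 |
| .256 | .53 | 0.512 | 0.50 to 0.53 |

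On a common method the drop is 0.640 − 0.512 = 0.128, about 13 points. That is well beyond the plan's simulation error. Rounding matters slightly: r = .26 gives 0.53 to 0.54, so 0.51 belongs with the unrounded .256.

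**Step 4: hand check.** Approximate power as the chance that both paths are significant.

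- Path a, by Fisher's z: atanh(0.30) × √57 = 2.34, so power is Φ(2.34 − 1.96) = 0.65. With .256 the statistic is 1.98 and power is 0.51.
- Path b at r_XM = 0.30: b = (0.50 − 0.30 × 0.20) / 0.91 = 0.484 with standard error 0.120, a ratio of 4.03 and power 0.98. At .256 the ratio is 4.06 and power is again 0.98.
- Products: 0.647 × 0.981 = 0.63 and 0.507 × 0.982 = 0.50.

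Path b is almost certain to be detected in either case. The Aim 3 power is therefore essentially the power of the condition-to-fit path, which is the input in dispute.

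**The case against.** **The source has not been seen.** Reference 80 may report several effects, one of which could support r = 0.30. The word medium may also be a benchmark label, since d near .5 and r = 0.30 are the usual medium values on their own scales. This stands, and it is why the request is to reconcile or justify rather than to declare .256 the right value. It does not remove the point, because the plan attributes both figures to one source and explains neither.

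**The arithmetic is sound.** This also stands. The 0.62 follows approximately from its stated inputs, and what is in question is one input.

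**The plan already concedes low power.** True, and no sample size or analysis depends on the figure: section 3.8 says the size of this phase was set by timeframe, budget and the number of interested Generation 1 providers. The concession does not correct the stated number.

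Three stronger readings are tempting, and the documents do not support them.

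- A reader might infer that Aim 2's calculation rests on d = .53 and is inconsistent with Aim 3's. It does not. Aim 2 is a minimum detectable effect calculation with no assumed effect, and d = .53 appears only afterwards as a comparator.
- A reader might infer that the larger value was chosen to flatter Aim 3. Nothing shows this. The plan volunteers both the unfavourable d = .53 and an unfavourable power.
- A reader might lower the power further for 20% attrition. In section 3.8 that rate belongs to the original combined goal of 96 providers and 576 patients, and no attrition rate is given for the projected 60 providers.

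**Conclusion.** The point holds as an unexplained mismatch in one input. On the plan's own quoted effect of d = .53, Aim 3 power is about 0.51 (0.50 to 0.53 across simulation variants), against a stated 0.62 that recomputes as 0.64 to 0.66. This rests on an equal split of providers, a single-mediator model, and the other two correlations as stated.

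Both figures also treat the 60 providers as independent, whereas Aim 2 assumes an ICC of 0.20 for the same providers. They are therefore probably optimistic. The effect of clustering on Aim 3 was not computed, and section 4.5 plans a multilevel model with patient outcomes that a single-level calculation on 60 units does not represent. It would go too far to call 0.51 a proven upper bound.

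The plan's conclusion that Aim 3 may be underpowered is unchanged. What changes is the size of the shortfall.

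**What to change.** In section 3.8, reconcile the two uses of reference 80 in one of two ways:

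1. restate Aim 3 power at r = .256, about 0.51 with N = 60; or
2. state which result in reference 80 supports r = 0.30, and show power at both values.

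In either case, give the conversion from d to r with the assumed split. Add a sentence saying that the calculation treats the 60 providers as independent although Aim 2 assumes an ICC of 0.20, so the figure is probably optimistic.

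The cost is a short text change and one rerun of the same application. No analysis, sample size or participant is affected. The stated power becomes less favourable, or is shown as a range.
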